**Table 8-1 Assessment Schedule**

Epoch	Screening		Treatment																	Follow up		End of Study
Visit Name	Screening	Baseline	Treatment																	201	202	299
Visit Numbers 	1	2	101			102	103 	104		105		106		107			108		201	202	299	
Days	-28 to -2	-1 to 1	1			2	3	8		15		22		29			36		43	57	71	
Time (post-dose)	-	-	0h 	CCI	1h	4h	24h	48h	0h 	2-4h	0h 	2-4h	0h 	2-4h	0h 	0.67h 	2-4h	0h 	2-4h	-	-	-
Informed consent	X																					
Inclusion / Exclusion criteria	X	X																				

Commercially Confidential Information

Medical history/current medical conditions	X																					
Alcohol Test and Drug Screen	S 		S 																			
Hepatitis and HIV Screen	S 																					
Pregnancy and assessments of fertility 	X 	X 												X 						X 	X 	
Demography	X																					
Body Height	X																					
Body Weight	X																				X	
Physical Examination	S 																				S	
Vital signs and body measurements	X	X	X		X	X 	X	X	X	X 	X	X 	X	X 	X	X	X 	X	X 	X		

Epoch	Screening		Treatment																	Follow up		End of Study	
	Screening	Baseline	Treatment																	201	202		
Visit Numbers 	1	2	101				102	103 	104		105		106		107			108		201	202	299	
Days	-28 to -2	-1 to 1	1				2	3	8		15		22		29			36		43	57	71	
Time (post-dose)	-	-	0h 	CCI	1h	4h	24h	48h	0h 	2-4h	0h 	2-4h	0h 	2-4h	0h 	0.67h 	2-4h	0h 	2-4h	-	-	-	
Maudsley Treatment Inventory	X																						
Sydney Melancholia Prototype Index	X																						
Melancholia and Mixed Depression Diagnostic Checklist	X																						
Concomitant therapies	X	X	X 				X	X	X		X		X		X			X		X	X	X	
Montgomery-Asberg Depression Rating Scale	X	X	X 		X		X	X	X		X		X		X			X		X	X	X	
Bech Rafaelsen Melancholia Scale		X	X 		X		X	X	X		X		X		X			X		X	X	X	
CORE Melancholia Scale		X	X 		X		X	X	X		X		X		X			X		X	X	X	
Young Mania Rating Scale		X	X 		X		X		X		X		X		X			X		X	X	X	
Clinical Global Impression of Severity		X	X 		X		X	X	X		X		X		X			X		X	X	X	

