 Additional pregnancy testing may be performed at each visit to meet local requirements.

 Serum pregnancy test

 Urine pregnancy test

 Not to be repeated if baseline visit and V101 are conducted on the same day.

Commercially Confidential Information

 24 hours after start of the first infusion

 V103 48 hours is an optional visit, however if V103 is conducted, all assessments should be completed.

 Assessments to be conducted once between 2 and 4 hours, and at 6 hours if there is an extended stay.

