### **12.5.2 Safety endpoints**

For all safety analyses, the safety set will be used. All listings and tables will be presented by treatment group.

Safety summaries (tables, figures) include only data from the on-treatment period with the exception of baseline data which will also be summarized where appropriate (e.g. change from baseline summaries). In addition, a separate summary for death including on treatment and post treatment deaths will be provided. In particular, summary tables for AEs will summarize only on-treatment events, with a start date during the on-treatment period (treatment-emergent AEs).

The on-treatment period lasts from the date of first administration of study treatment to 30 days after the date of the last actual administration of any study treatment.

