### **Clinical laboratory evaluations**

All laboratory data will be listed by treatment group, subject, and visit/time and if normal ranges are available abnormalities will be flagged. Summary statistics will be provided by treatment and visit/time. Shift tables using the low/normal/high/ (low and high) classification will be used to compare baseline to the worst on-treatment value.

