7.1 Variables

Adverse events, vital signs (blood pressure, pulse rate, body temperature), ECG intervals, laboratory measurements, Sheehan suicidality scale score, as well as subject demographics, baseline characteristics, and treatment information.

Baseline is defined to be the last available measurement obtained before the first infusion on Day 1.

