7.1.1 Descriptive analyses

Subject demographics and other baseline characteristics

All data for background and demographic variables will be listed by treatment group and subject. Summary statistics will be provided by treatment group.

Relevant medical history, current medical conditions, results of laboratory screens, drug tests and any other relevant information will be listed by treatment group and subject.

Treatment

Data for study drug administration (rescue medication) and concomitant therapies will be listed by treatment group and subject.

Vital signs

All vital signs data will be listed by treatment, subject, and visit/time and if ranges are available abnormalities (and relevant orthostatic changes) will be flagged. Summary statistics will be provided by treatment and visit/time.

The below descriptive analysis will be conducted on the following two blood pressure (BP) parameters and their change from baseline: SBP and DBP.

- A separate summary statistics (quantitative) of raw values and change from baseline values will be provided by treatment group and timepoint.
- Summary tables of categorical analyses will be produced displaying the number and percentage of subjects with notable BP observations (irrespective of the timepoint) using the following categories:
 - SBP <90 mmHg;
 - SBP >140 mmHg;
 - SBP increase from baseline >20 mmHg;
 - SBP decrease from baseline >20 mmHg;
 - DBP <50 mmHg; DBP >90 mmHg;
 - DBP increase from baseline >20 mmHg;
 - DBP decrease from baseline >20 mmHg

These categorical analyses will be provided for each treatment group

Commercially Confidential Information

For criteria with change from baseline, only measurements occurring after 1st injection on Day 1 will be included. For other criteria, both baseline and post-baseline measurements will be included. All scheduled and unscheduled visits will be used for this summary table.

ECG evaluations

All ECG data will be listed by treatment, subject and visit/time, abnormalities will be flagged. Summary statistics will be provided by treatment and visit/time.

Clinical laboratory evaluations

All laboratory data will be listed by treatment, subject, and visit/time and if normal ranges are available abnormalities will be flagged. A separate listing is provided presenting all parameters in a subject with any abnormal values. Summary statistics will be provided by treatment and visit/time.

Adverse events

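### The visible rule for the absolute-limit rows of the notable blood-pressure table merges baseline and later readings, so the rows do not show how many counted subjects were already beyond the limit before dosing

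*SAP*

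**What the plan says.** SAP 7.1.1 (Vital signs) plans a summary of the "number and percentage of subjects with notable BP observations (irrespective of the timepoint". There are eight criteria: four absolute limits (SBP <90, SBP >140, DBP <50, DBP >90 mmHg) and four changes from baseline of more than 20 mmHg.

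The change rows use only readings after the first dose. The absolute-limit rows follow a different rule: "For other criteria, both baseline and post-baseline measurements will be included". The SAP adds: "All scheduled and unscheduled visits will be used for this summary table". SAP 7.1 fixes baseline as a pre-dose value: "Baseline is defined to be the last available measurement obtained before the first infusion on Day 1".

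Three other provisions bear on the point:
- Protocol 12.5.2 limits safety summaries to on-treatment data, "with the exception of baseline data which will also be summarized where appropriate (e.g. change from baseline summaries".
- For laboratory data, Protocol 12.5.2 plans shift tables that "will be used to compare baseline to the worst on-treatment value". No such table is visible for blood pressure.
- SAP 7.1.1 separately plans listings by subject and visit/time, and quantitative summaries of raw values and changes by treatment group and timepoint.

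A redacted block stands directly before the rule on which readings count.

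**The concern.** A subject above 140 mmHg before the first infusion and a subject who first exceeds 140 mmHg after it add the same one to the same row. The row alone does not tell a reader which was which.

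The distinction is worth having here for two reasons. The exclusion criteria in Protocol 5.2 set no blood-pressure limit, so subjects can enter already above 140 or 90 mmHg. Protocol 4.5 also reports that depression trials of low-dose ketamine consistently show transient rises in blood pressure during infusion and for up to 80 minutes after dosing, so readers will look at blood pressure in this trial. This is the only visible table that counts subjects beyond an absolute limit.

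What is at stake is how easily one descriptive safety table can be read. Efficacy is not touched.

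**Working it through.** The documents give no figure for this point, so there is none to reproduce. The check has two parts.

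**1. Text.** Of the eight criteria, the four change rows are post-dose only and the four absolute rows are not. The visible text has no baseline-only count, no post-dose-only count and no blood-pressure shift table.

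**2. Size.** The only input from the documents is the number of readings. Protocol Table 8-1 shows these vital-sign times after the start of the first infusion:
- Days 1 to 3: 1h, 4h, 24h and 48h = 4
- V104, V105, V106: two each = 6
- V107: 3; V108: 2; V201: 1
- Total k = 4 + 6 + 3 + 2 + 1 = 16, or 15 if the optional 48h visit is not held ("V103 48 hours is an optional visit, however if V103 is conducted, all assessments should be completed").

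Sixteen is not a maximum. Footnote 13 adds a 6h reading for extended stays, and unscheduled readings also count.

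Assumptions (not in the documents): reading = subject mean m + independent error, with m ~ N(μ, σb²), error SD σw and no drug effect. Main case for SBP: σb = 11, σw = 8, μ = 120, 125 or 130 mmHg. Write q(m) = Φ((140 − m)/σw) for the chance that one reading is not notable. Then:
- notable at baseline: B = 1 − E[q]
- notable at any time after dosing: P = 1 − E[q^k]
- counted in the planned row: R = 1 − E[q^(k+1)]
- notable only before dosing: R − P
- share of the row already notable at baseline: B/R
- newly notable among the rest: (R − B)/(1 − B)

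Results for SBP >140, k = 16:

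| Mean SBP | B | P | R | R − P | B/R | (R − B)/(1 − B) |
|---|---|---|---|---|---|---|
| 120 | 7.1% | 30.9% | 31.5% | 0.65% | 22% | 26% |
| 125 | 13.5% | 46.9% | 47.7% | 0.75% | 28% | 39% |
| 130 | 23.1% | 63.5% | 64.3% | 0.73% | 36% | 54% |

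For example, at mean 120, B/R = 7.1/31.5 = 22% and (31.5 − 7.1)/(100 − 7.1) = 26%.

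With equal arms of 66/6 = 11 (an assumption, because the ratio is redacted), the row would count about 3.5, 5.2 or 7.1 subjects, of whom 0.8, 1.5 or 2.5 were notable at baseline.

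Sensitivity:
- k = 15: B/R is 23%, 29%, 36%.
- Other SDs (σb/σw = 11/5, 11/11, 14/8, 8/8): B/R runs from 15% to 44%, R − P from 0.3% to 1.0%, and newly notable from about 12% to 70%.
- An assumed rise of 10 mmHg at the Day 1 1h reading and the V107 0.67h reading: B/R is 17%, 23%, 32%.
- DBP >90 (SDs 8/6, means 75, 78, 82): B/R is 22%, 26%, 34%.
- SBP <90 and DBP <50 (same SDs and means): at most 1.4% are notable at baseline.

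The share depends heavily on the assumptions. If instead 5%, 10%, 20% or 30% (b) are beyond a limit at baseline and only 10% (c) of the rest cross it later, b/(b + (1 − b)c) gives 34%, 53%, 71% or 81%.

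**The case against.** The case against giving this much weight is strong, and most of it stands.

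- **Redaction.** The block before the rule is a natural place for a further breakdown, and the SAP's list of tables is redacted too. A reader might infer that the plan has no split by period. The documents cannot support that; they show only that the visible rule pools the readings.
- **No breach.** A reader might infer a conflict with the protocol's on-treatment restriction. There is none, because Protocol 12.5.2 lets baseline data be summarized where appropriate. The SAP rule is also explicit and reproducible.
- **Little distortion of the count.** A reader might infer that pre-dose readings inflate the row. They hardly do: subjects notable only before dosing are at most 1.0% in the cases tried, or about 0.1 subject in an arm of 11. Most subjects notable at baseline are notable again later.
- **Other outputs.** The change rows measure a within-subject rise directly, after dosing only. By-timepoint summaries and listings are planned, and Protocol 12.5.2 flags clinically notable values where ranges exist. With about 66 subjects, baseline status can be recovered from the listing. The placebo arm is counted under the same rule.
- **Assumed inputs.** The model treats errors as independent, although readings within a visit may be correlated. Protocol 8.4 makes each value the mean of three measurements, so the SDs refer to that mean. The percentages illustrate the point and are not evidence about this trial.

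What remains is narrow. Listings need reconstruction by hand, by-timepoint summaries give no count beyond a limit, and a rise of more than 20 mmHg is a different question from crossing 140 or 90 mmHg.

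**Conclusion.** The point holds as a low-severity, cheap improvement. On the visible text, the absolute-limit rows do not separate findings present before dosing from those first seen after it. In practice only the two high-limit rows matter.

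Under the main assumptions, roughly a quarter to a third of subjects counted for SBP >140 would already have been above it at baseline (15% to 44% over the SDs tried). The blood-pressure means, SDs and arm size are assumed; only the number of scheduled readings comes from the documents. The conclusion is also conditional on the redacted block, which may already provide the split.

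The gap is in what the row tells the reader. The total itself is close to a post-dose-only count. Nothing visible in the documents makes a test, a stopping rule or the primary conclusion depend on this table.

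**What to change.** In SAP 7.1.1, replace the sentence on the other criteria with a rule such as:

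*For absolute thresholds, the table will report by treatment group: (a) the number of subjects notable at baseline; (b) the number notable at any time after the start of the first infusion, among all subjects in the safety set; (c) the number newly notable after the start of the first infusion, among subjects not meeting that criterion at baseline.*

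A baseline-to-worst post-dose shift table, on the model the protocol already uses for laboratory data, would be equivalent. If the redacted block already gives this split, only the wording needs aligning. Simply removing baseline readings from the count would not supply the missing information.

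The cost is one sentence and a slightly longer table; all readings are already collected. Row (c) has a drawback that should be stated with it: it sets one baseline reading against about 16 scheduled later ones, plus any 6h and unscheduled readings. It therefore labels many subjects newly notable with no drug effect, and its denominators are smaller and differ by arm. It should be read against placebo and beside rows (a) and (b), not as a clean treatment-emergent count.

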### **3 Study design**

This is a non-confirmatory, multi-center, 6-treatment arm in the European countries and 5-treatment arm in the USA (no ketamine arm), randomized, subject and investigator blinded, parallel group, placebo controlled study in treatment-resistant depression patients. The study will randomize approximately 66 Subjects and while the study design utilizes an outpatient visit schedule, the study allows for the inclusion of subjects seeking treatment for their disease from both an 'inpatient' or 'outpatient' clinic setting.

A screening period of maximum 4 weeks will be used to assess eligibility. Patients who meet the eligibility criteria at screening will proceed to baseline evaluations on Day-1 or Day 1. All baseline safety evaluation results must be available prior to randomization. At the baseline visit, eligible subjects will be randomized to one of the treatment arms. Randomized subjects will enter a 36- day treatment period, receiving at each treatment visit, a 40-minute infusion with a safety observation period of 2-4 hours (i.e. a minimum of 2 hours) post the start of

infusion. If the subject reports no dissociative symptoms and no suicidal symptoms, the subject will be allowed to leave the clinical treatment setting. Visits to assess efficacy and safety are scheduled at 24 hours, 48 hours (if applicable) and every week during the treatment period. If 48 hour visit (V103) is conducted, then all assessments should be completed. The assessment to address the primary objective will be performed at 24 hour post-dose. Safety assessments will include physical examinations, ECGs, vital signs, standard clinical laboratory evaluations (hematology, blood chemistry, and urinalysis), adverse event and serious adverse event monitoring. At the conclusion of the treatment period (Day 1 - Day 36), subjects will enter a 5-week follow up period consisting of two follow visits approximately 1 week (Day 43) and 3 weeks (Day 57) after the last study drug administration and an end of study completion visit (Day 71) The total duration for each subject in the study is maximum 14-weeks including screening and baseline. No interim analysis is planned. The study design is summarized in [Figure 3-1](#) below for the European countries (same study design without the ketamine arm in the USA).

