## 10 Safety monitoring and reporting

### 10.1 Definition of adverse events and reporting requirements

#### 10.1.1 Adverse events

An adverse event (AE) is any untoward medical occurrence (e.g., any unfavorable and unintended sign [including abnormal laboratory findings], symptom or disease) in a subject or clinical investigation subject after providing written informed consent for participation in the study. Therefore, an AE may or may not be temporally or causally associated with the use of a medicinal (investigational) product.

The investigator has the responsibility for managing the safety of individual subject and identifying adverse events.

Novartis qualified medical personnel will be readily available to advise on trial related medical questions or problems.

The occurrence of adverse events must be sought by non-directive questioning of the subject at each visit during the study. Adverse events also may be detected when they are volunteered by the subject during or between visits or through physical examination findings, laboratory test findings, or other assessments.

Adverse events must be recorded in the Adverse Events CRF under the signs, symptoms or diagnosis associated with them, accompanied by the following information (as far as possible) (if the event is serious refer to [Section 10.1.2](#)):

1. The Common Toxicity Criteria (CTC) AE grade (version 5.0 or higher). A copy of the CTCAE grading will be provided separately in the SOM.

Adverse events will be assessed and graded according to the Common Terminology Criteria for Adverse Events (CTCAE) version 5.0

2. its relationship to the study treatment and other investigational treatment. If the event is due to lack of efficacy or progression of underlying illness (i.e. progression of the study indication) the assessment of causality will usually be 'Not suspected'. The rationale for this guidance is that the symptoms of a lack of efficacy or progression of underlying illness are not caused by the trial drug, they happen in spite of its administration and/or both lack of efficacy and progression of underlying disease can only be evaluated meaningfully by an analysis of cohorts, not on a single subject
3. its duration (start and end dates) or if the event is ongoing, an outcome of not recovered/not resolved must be reported.
4. whether it constitutes a SAE (see [Section 10.1.2](#) for definition of SAE) and which seriousness criteria have been met

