5. action taken regarding with study treatment.

All adverse events must be treated appropriately. Treatment may include one or more of the following:

- Dose not changed
- Dose Reduced/increased
- Drug interrupted/withdrawn

6. its outcome.

Conditions that were already present at the time of informed consent should be recorded in medical history of the subject.

Adverse events (including lab abnormalities that constitute AEs) should be described using a diagnosis whenever possible, rather than individual underlying signs and symptoms.

Adverse event monitoring should be continued for at least 30 days following the last dose of study treatment.

Once an adverse event is detected, it must be followed until its resolution or until it is judged to be permanent (e.g. Continuing at the end of the study), and assessment must be made at each visit (or more frequently, if necessary) of any changes in severity, the suspected relationship to the interventions required to treat it, and the outcome.

Information about adverse drug reactions for the investigational drug can be found in the Investigator Brochure (IB).

Abnormal laboratory values or test results constitute adverse events only if they fulfill at least one of the following criteria:

- they induce clinical signs or symptoms
- they are considered clinically significant
- they require therapy

Clinically significant abnormal laboratory values or test results must be identified through a review of values outside of normal ranges/clinically notable ranges, significant changes from baseline or the previous visit, or values which are considered to be non-typical in subjects with the underlying disease.

Follow the instructions found in the SOM for data capture methodology regarding AE collection for subjects that fail screening.

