#### **Adverse events**

All information obtained on AEs will be displayed by treatment group and subject.

The number (and percentage) of subjects with treatment emergent AEs (events started after the first dose of study medication or events present prior to start of double-blind treatment but increased in severity based on preferred term) will be summarized in the following ways:

- by treatment, primary system organ class and preferred term;
- by treatment, primary system organ class, preferred term and maximum severity;
- by treatment, Standardized MedDRA Query (SMQ) and preferred term.

Separate summaries will be provided for study medication related AEs, death, SAEs, other significant AEs leading to discontinuation.

The incidence of psychotomimetic AEs will be tabulated by treatment group, according to severity and relationship to drug.

A subject with multiple AEs within a primary system organ class is only counted once towards the total of the primary system organ class.

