All information obtained on adverse events will be displayed by treatment group and subject.

Summary tables for AEs will summarize only on-treatment events, with a start date during the on-treatment period (treatment-emergent AEs). The on-treatment period lasts from the date of first administration of study treatment to 30 days after the date of the last actual administration of any study treatment.

The number and percentage of subjects with adverse events and drug-related adverse events will be separately tabulated, by body system and preferred term with a breakdown by treatment. A subject with multiple adverse events within a body system is only counted once towards the total of this body system and treatment.

In addition, the number and percentage of subjects with adverse events will be tabulated by body system, preferred term, maximum severity with a breakdown by treatment group. A subject with multiple severity ratings for an AE under treatment, is only counted under the maximum rating.

Summary tables to show the frequency of subjects affected, time (in hours) of onset and resolution time (in hours) by treatment (MIJ821 0.16 mg/kg pooled, MIJ821 0.32 mg/kg pooled and placebo) and total, will be provided for AEs of interest (dissociation, amnesia, dissociation and amnesia (together), sedation and vomiting).

For these summary tables of AEs of interest, the following guidelines will be applied:

1. Frequency / time to onset / time to resolution of AEs of interest:
 - Frequency - A subject with multiple AEs with the same preferred term (PT) is counted only once for that PT
 - Time to onset – A subject with multiple events in a preferred term of interest, we are only considering the first instant
 - Time to resolution – A subject with multiple events in a preferred term of interest, we are only considering the maximum of the AE duration

2. For subjects who experienced ‘Dissociation and amnesia’:
 - Time to onset – we will use time to 1st instant (whether it’s dissociation or amnesia)
 - Time to resolution – we will use maximum of the AE duration (whether it’s dissociation or amnesia)

3. Based on the consultation with the clinical team, the following rules for grouping of the AEs of interest were elicited:

AE of interest	Notes
Sedation	See AE grouping below
Dissociation	See AE grouping below + ‘dissociative amnesia’
Amnesia	Any term that includes ‘amnesia’, except for ‘dissociative amnesia’ which falls under ‘Dissociation’

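### Protocol 12.5.2 defines treatment-emergent AEs in two incompatible ways and SAP 7.1.1 adopts only the start-date rule, so an AE that arises before dosing and worsens after it may be left out of the summary tables

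*SAP*

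**What the plan says.** Three places define the same term.

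- **Protocol 12.5.2, opening text.** The AE tables are limited to events "with a start date during the on-treatment period (treatment-emergent AEs". There is no provision for worsening.
- **Protocol 12.5.2, Adverse events subsection.** Besides events that begin after the first dose, it counts "events present prior to start of double-blind treatment but increased in severity based on preferred term".
- **SAP 7.1.1, Adverse events.** "Summary tables for AEs will summarize only on-treatment events, with a start date during the on-treatment period (treatment-emergent AEs". The period is then fixed: "The on-treatment period lasts from the date of first administration of study treatment to 30 days after" the last administration. The visible SAP text on AEs, including the rules for the ClinicalTrials.gov and EudraCT tables, contains no worsening clause.

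On collection, Protocol 10.1.1 defines an AE as something occurring in a "subject after providing written informed consent for participation in the study", so records can exist before dosing. Protocol 3 sets the length of that window: "A screening period of maximum 4 weeks will be used to assess eligibility". Once an AE is detected, Protocol 10.1.1 has it followed until it resolves or is judged permanent, and an "assessment must be made at each visit (or more frequently, if necessary) of any changes in severity". Conditions already present at consent go to medical history instead.

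**The concern.** The SAP states that it implements the analysis planned in the protocol, yet it drops one of the protocol's two definitions without comment. An AE that begins in screening and gets worse after an infusion meets the Adverse events subsection of Protocol 12.5.2. It fails the start-date rule if it is still carried under its pre-dose start date.

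Safety and tolerability is a named secondary objective with AE incidence as an endpoint (Protocol Table 2-1, SAP 1.3.2). The registry tables also depend on treatment-emergent status. If the choice between the definitions is left open until the data are unblinded, it could be made with the counts by arm in view.

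**Working it through.** No figure in the plan needs reproducing. The check compares the rules case by case and then gives an illustration of scale.

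**Step 1. Classify each course of events, read at the level of the event.**

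| Course of the event | Worsening rule (Protocol 12.5.2, Adverse events) | Start-date rule (Protocol 12.5.2 opening; SAP 7.1.1) |
|---|---|---|
| Starts after first infusion | counted | counted |
| Starts in screening, severity unchanged | not counted | not counted |
| Starts in screening, worsens after dosing, one record with the pre-dose start date | counted | **not counted** |
| Starts in screening, worsens after dosing, new record opened at worsening | counted | counted |
| Starts in screening, improves after dosing, new record opened at any grade change | not counted | **counted** |

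The rules disagree in the third and fifth rows. They agree throughout only if a new record is opened on worsening and on no other grade change.

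**Step 2. Find the recording convention.** Protocol 10.1.1 asks for a CTCAE grade and for start and end dates for each AE, and for changes in severity to be assessed at each visit. It does not say whether a change in grade updates the existing record or closes it and opens another. Operational detail is deferred to the Site Operations Manual, which is not among the documents. The third and fifth rows therefore both remain possible.

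**Step 3. Scale of one misclassified subject.** Inputs: about 66 subjects (Protocol 3 and 5) and six arms in Europe, five in the USA (Protocol 3). The allocation is redacted, so arm size is an assumption.

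- Average over six arms: 66/6 = 11 subjects, and 1/11 = 9.1 percentage points.
- Assumed range of 8 to 16 subjects: 1/8 = 12.5 points, and 1/16 = 6.25, about 6.3 points.

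These figures hold only if the subject has no other qualifying event in the same table row, because a subject counts once per row.

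**Step 4. Registry threshold.** SAP 7.1.1 tabulates non-serious treatment-emergent AEs with an incidence above 5%. If that is applied by arm, one subject in an arm of 8 to 16 exceeds it (6.3% to 12.5%) and can decide whether a preferred term is listed. If it is applied to all subjects, one is 1/66 = 1.5% and does not reach it alone. The visible text does not say which denominator applies.

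**The case against.** The strongest reply is that the gap may be closed by how AEs are recorded. The SAP's registry rules merge consecutive AEs of the same class and preferred term when the gap is one day or less, whatever their severity. Such a rule fits a database that opens a new record when the grade changes. The SAE definition in Protocol 10.1.2 also treats worsening of a pre-existing sign as an event in itself. A new record opened after dosing would carry an on-treatment start date and be tabulated.

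This stands as far as it goes: omission is conditional on the recording convention. It does not rescue the start-date rule. If every grade change splits a record, an event that only improves after dosing acquires an on-treatment start date and is counted. Nor does the SAP say how a block of consecutive records spanning the first infusion is classified.

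Three further limits also stand. Conditions present at consent go to medical history, so only AEs arising between consent and first infusion are affected. Suicidality, dissociation and mania are measured on scheduled scales with a baseline, independently of AE start dates. And SAP 7.1.1 displays all AE information by treatment group and subject, so the events remain visible.

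A reader might infer that worsened screening events are certain to disappear from the safety tables, or that incidence is biased downward by a known amount. The documents support neither. Protocol 10.1.1 requires severity changes to be assessed but does not say that the original record and start date are kept. No rate of such events can be derived, and under split records the error can run upward.

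**Conclusion.** The contradiction is certain: it lies in unredacted text, within one protocol section and again between that section's Adverse events subsection and the SAP. Its effect on the tables is conditional. An AE first arising between consent and first infusion and worsening after dosing is left out of the SAP summary and registry tables if its record keeps the pre-dose start date. The number affected is unknown. For each misclassified subject the shift is about 6 to 12.5 percentage points in an arm, on assumed arm sizes of 8 to 16. In a non-confirmatory study with full listings this does not threaten the primary result. It does leave undetermined which events count towards a secondary endpoint, and it should be settled before unblinding.

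**What to change.** Use one definition in the opening text of Protocol 12.5.2, its Adverse events subsection and SAP 7.1.1. An AE is treatment-emergent if it starts on or after the first infusion, or was present before the first infusion and has a higher CTCAE grade after it, by preferred term, up to 30 days after the last dose.

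- **Derivation.** Compare the maximum post-dose grade with the last pre-dose grade for the same preferred term. Treat records that run on from one another as one event; the SAP's one-day gap rule could serve. This holds whether severity is tracked within one record or split across several, and it does not count an event that only improves.
- **Data check.** Confirm that the eCRF keeps the grade as it stood before the first infusion. If it stores only one grade per record, state how worsening is to be recorded.
- **Scope.** Apply the definition to the AE incidence and registry tables. In the tables of time to onset and resolution, which are in hours, use the date and time of worsening or exclude events that started before dosing. Otherwise onset times would be negative.

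The cost is one or two sentences in the SAP, a programming flag, and a change to the protocol wording, which Protocol 14.1 requires to be made by written amendment. Reported AE counts may rise slightly.
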